Subjects should also meet other inclusion and none of the exclusion criteria necessary for the study and, if needed, a blood screen for liver function and full blood cell count will be carried out. Pregnant or breast-feeding women, women of child-bearing potential who do not agree to the contraceptive methods needed for participating in the trial will be excluded. Women of child-bearing potential must meet the MHRA pregnancy prevention programme and agree to an annual risk acknowledgement plan for pregnancy prevention. A pregnancy test must be negative for all women of childbearing potential to participate in the trial. Also, patients who pose immediate or significant risk for suicide will be excluded.

The screening must occur prior to randomization to the study and the study medication will not start within 24 hours of written consent. If the screening could not be completed within 8 weeks from the day of the signed consent, then inclusion criteria will be reassessed by the investigator and clinical tests will be redone if judged necessary by the research team. The eight-week period will then again apply for the reassessment and it will be the final attempt to include the subject under the consent that was obtained. Assessments at the screening stage are described in the Trial Schedule (Table 1).

Treatment period (Week 0 - 52 followed by discontinuation period)

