- 2 the annual pregnancy risk assessment form should be checked for completion at baseline. It is valid for one year from the date of signature by the subject and hence it may need repetition during the course of the clinical trial and hence at V5 make sure it is valid till the end of their medication phase
- 3 Optional at clinician discretion (e.g. if there is a gap or change in contraception)
- 4- Assess changes from baseline that require clinical review (e.g. new onset liver disease, new prescription)
- 5-To collect a sample if not already collected at screening
- &Check if subjects have a HoNOS file, if not create one in co-ordination with their clinical team. * HoNOS will be collected on an annual basis till end of trial
- ** Only if needed to complete the down titration.
- £ To be performed at the discretion of the clinician based on clinical history and medical assessment.
- # Unscheduled UKU should be administered if a subject develops a side-effect requiring treatment.
- \$ All assessments at baseline (V2) must be performed pre-dose. Also, a minimum of 24 hours between signing of ICF and dosing will be given for subjects to reflect on their participation.
- % V7 to be scheduled within 1 week after stopping study medication & includes a single follow up via telephone or face-to-face 60 days since their last study drug intake to record for any AEs/SAEs. Most will be further followed up using electronic notes. The last patient who completes V7 (including the 60 day AE/SAE assessment) will result in the end of the trial.

5 Trial Medication

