6.5 Withdrawal of Subjects

Participants have the right to withdraw from the study at any time for any reason. The investigator also has the right to withdraw patients from the study drug in the event of inter-current illness, AEs, SAE's, SUSAR's, protocol violations, cure, administrative reasons or other reasons. SAE's and SUSAR's will be followed up until resolution and outcomes will be recorded for the DMEC and TSC to review. It is understood by all concerned that an excessive rate of withdrawals can render the study un-interpretable; therefore, unnecessary withdrawal of patients should be avoided. In the event of hospitalization of patients unrelated to the study drug, patients will be reviewed for their continuation in the study and, if needed, will be recommended for a drug holiday as described in the next paragraph. Should a patient decide to withdraw from the study, the reason for withdrawal will be recorded in the exit interview if they provide us with one. Should a patient discontinue from study drug only, efforts will be made to continue to obtain follow-up data, with the permission of the patient.

Poor compliance (no minimum threshold) will not merit withdrawal but will be recorded and follow-up data will be continued to be obtained. Study drug holiday is permissible in case of an emergency, or for elective surgery or medical procedures. The process for the drug holiday is that when subjects will undergo a down titration till IMP is completely stopped as described in Section 4.3 and will then be up titrated when they re-join the

study. In such cases their assessments will be delayed depending on the study drug holiday period.

6.6 Expected Duration of Trial.

The total duration of the trial is expected to be 5 years. The end of the trial will be defined as last patient to complete visit 7 (V7), including the 60-day follow-up period to assess AE/SAEs after the last day of medication. Each individual subject will remain on the active trial for 12 months, +/- two weeks for the discontinuation of the treatment at the end. Long-term annual follow-up using clinical and electronic records will be conducted up to the point where the last patient completes Visit 7 for the entire trial.

7 Trial Procedures

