7.1 By Visit

ATLANTIS study visits

Visit 1: Face-to-face consenting and screening visit (approximately -8 to 0 weeks)

Following a telephonic or face-to-face conversation and provision of information on the study, subjects will be invited for consenting and screening. A unique screening number will be assigned to each subject.

Subjects will be evaluated during the face-to-face screening visit to determine their eligibility to enrol in the study after obtaining their consent.

The following procedures will be performed at Screening:

- Explain study procedures
- Obtain signed informed consent, capacity assessment and privacy authorization from the subject before conducting any other visit procedures
- Collect demographic information
- Review inclusion and exclusion criteria (conduct clinical interview using SCID-5 and PANSS)
- Conduct frailty assessment if needed
- Record medical and psychiatric history
- Record current and past medication use
- Conduct Medication Adherence Rating Scale (for antipsychotic medication)
- Conduct Risk assessment using the Columbia Suicide Severity Rating scale
- Record vital signs (blood pressure/pulse rate)
- Record height and weight

- Collect blood sample for clinical laboratory assessments (full blood count, liver function test if needed based on medical history)
- For female subjects, collect serum/ urine samples for pregnancy tests
- For female subjects of childbearing potential, review their current choice of contraception
- Complete the pregnancy annual risk Acknowledgement form for female subjects
 of childbearing potential if not completed yet (if serum pregnancy test needs to
 be done then conduct one)
- Collect blood samples for pharmacogenomics, epigenetics, antipsychotic drug levels

Visit 2 & DS1: Day 1: Baseline measures and Valproate titration begins (week 0)

- Review inclusion and exclusion criteria
- Review recent medical and medication history for changes since screening visit
- Conduct Medication Adherence Rating Scale (for antipsychotic medication)
- Risk assessment using the Columbia Suicide Severity Rating scale (baseline assessment)
- Conduct clinical interviews/assessments (PANSS, CGI-SCH, CDSS, YMRS, MOAS, SWEMBS, SF-36, CSRI, UKU)
- Record weight
- Record vital signs (blood pressure/pulse rate)
- Collect blood samples for pharmacogenomics, epigenetics, antipsychotic drug levels and other measures before IMP ingestion if not collected earlier

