- Ensure female participants use effective long-term methods of contraception during the course of the study
- Explain the drug titration process
- Randomise the patient
- Dispense 2 weeks of medication (completed annual risk acknowledgment form will be needed for female subjects of childbearing potential prior to dispensing)
- Follow up after one week (via telephone/face to face) to check on how the
 patient is progressing with drug titration and also check if there are any concerns

Visit 3 & DS2: Face-to-face 2-week visit (week 2)

- Review recent medical and medication history for changes since previous visit
- Record vital signs (blood pressure/pulse rate)
- Remind female participants to continue to use effective long-term methods of contraception during the study

- If there is a gap in contraception or if the contraceptive method has been changed then conduct a urine pregnancy test before dispensing study medication
- Conduct Medication Adherence Rating Scale (for antipsychotic medication)
- Conduct a pill count of the IMP
- Dispense 3 months of medication (check if completed annual risk acknowledgment form for female subjects of childbearing potential remains valid)
- Where the target dose has not been reached, and where an increase in dose is executed at this visit then a telephone call/face-to-face visit to check on tolerability to be conducted after approximately three days.

Visit 4 & DS3: 3-month visit (week 13)

- Obtain medical and medication history since the last visit
- Conduct Medication Adherence Rating Scale (for antipsychotic medication)
- Risk assessment using the Columbia Suicide Severity Rating scale
- Conduct clinical interviews (PANSS, CGI-SCH, CDSS, YMRS, MOAS, SWEMBS, SF-36, CSRI, UKU)
- Record weight
- Record vital signs (blood pressure/pulse rate)
- Collect blood sample for clinical laboratory assessments (full blood count, liver function test)
- Collect blood samples for pharmacogenomics, epigenetics and drug levels (antipsychotic and valproate) and other measures
- Remind female participants to continue to use effective long-term methods of contraception during the study
- If there is a gap in contraception or if the contraceptive method has been changed then conduct a urine pregnancy test before dispensing study medication
- Conduct a pill count of the IMP
- Dispense 3 months of medication (check if completed annual risk acknowledgment form for female subjects of childbearing potential remains valid)

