- If an increase in dose is executed at this visit then a telephone call to check on tolerability to be conducted after three days

Visit 5 & DS4: 6-month visit (week 26)

- Obtain medical and medication history since last visit
- Conduct Medication Adherence Rating Scale (for antipsychotic medication)

- Risk assessment using the Columbia Suicide Severity Rating scale
- Conduct clinical interviews (PANSS, CGI-SCH, CDSS, YMRS, MOAS, SWEMBS, SF-36, CSRI, UKU)
- Record height and weight
- Record vital signs (blood pressure/pulse rate)
- Remind female participants to continue to use effective long-term methods of contraception during the study
- If there is a gap in contraception or if the contraceptive method has been changed then conduct a urine pregnancy test before dispensing study medication
- Conduct a pill count of the IMP
- Dispense 3 months of medication (check if completed annual risk acknowledgment form for female subjects of childbearing potential remains valid at this time-point but also if it lasts till the end of medication phase and if needed perform a serum pregnancy test and complete a fresh annual risk acknowledgement form)

DS 5: 9-month dispensing session (week 36)

- Remind female participants to continue to use effective long-term methods of contraception during the study
- If there is a gap in contraception or if the contraceptive method has been changed then conduct a urine pregnancy test before dispensing study medication
- Conduct a pill count of the IMP
- Dispense 3 months of medication (check if annual risk acknowledgment form for female subjects of childbearing potential remains valid until end of trial)

Visit 6 & DS6: 12-month visit (week 52)

- Obtain medical and medication history since last visits
- Conduct Medication Adherence Rating Scale (for antipsychotic medication)
- Risk assessment using the Columbia Suicide Severity Rating scale
- Conduct clinical interviews (PANSS, CGI-SCH, CDSS, YMRS, MOAS, SWEMBS, SF-36, CSRI, UKU)
- Record weight
- Record vital signs (blood pressure/pulse rate)
- Collect blood sample for clinical laboratory assessments (full blood count, liver function test)
- Collect blood samples for pharmacogenomics, epigenetics and drug levels (antipsychotic and valproate)

- Remind female participants to continue to use effective long-term methods of contraception during the study

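### No pregnancy test is mandatory on the day valproate is first dispensed; the last required test can be about 8 weeks old, and the text conflicts on whether urine may replace serum

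*Protocol*

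**What the plan says.** **Entry.** Protocol Section 4.3 (screening period) states: "A pregnancy test must be negative for all women of childbearing potential to participate in the trial". It sets neither a day for the test nor a maximum age for the result. Pregnancy is exclusion criterion 3 in Section 6.2.

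**Schedule.** Table 1 marks the serum test at V1 and, under a footnote, at V5. Nothing is marked in that row at V2. The urine test is marked at V1 to V7, including V2, always with the footnote "3 Optional at clinician discretion (e.g. if there is a gap or change in contraception".

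**First dispensing.** The V2 list in Section 7.1 contains no pregnancy test. Its condition for women of childbearing potential is the form: "Dispense 2 weeks of medication (completed annual risk acknowledgment form will be needed for female subjects of childbearing potential prior to dispensing". The lists for V3, V4, V5, DS5 and V6 each add a conditional test; if there is a gap in contraception or "the contraceptive method has been changed then conduct a urine pregnancy test before dispensing study medication".

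**Screening overrun.** If screening is not finished within 8 weeks of consent, inclusion criteria are reassessed and "clinical tests will be redone if judged necessary by the research team. The eight-week period will then again apply for the reassessment".

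**Drug holiday.** Under Section 6.5, "subjects will undergo a down titration till IMP is completely stopped as described in Section 4.3 and will then be up titrated". No pregnancy test is mentioned at restart.

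**Test type.** Section 5.3, inclusion criterion 10 (Section 6.1) and Section 9.1 call for serum. The V1 list in Section 7.1 says "For female subjects, collect serum/ urine samples for pregnancy tests", and Section 9.1 goes on to offer urine to a patient who does not want to give blood.

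**The concern.** Section 5.3 names a risk to the unborn child and builds the pregnancy prevention programme around it. The moment that matters most is the first tablet. Yet a conception between V1 and V2 is found before that tablet only if someone chooses to test.

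If it is missed, the next scheduled serum test is at V5 (week 26), which Section 7.1 words as "if needed perform a serum pregnancy test and complete a fresh annual risk acknowledgement form". The next pregnancy test that Section 7.1 lists without a condition is at V6 (week 52). Any earlier detection depends on the discretionary urine test.

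The serum/urine conflict is a separate difficulty. A site faced with a woman who declines a blood sample cannot tell from the protocol whether a negative urine result makes her eligible.

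**Working it through.** No sample-size, power or alpha figure is involved. The check has three parts.

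**1. Age of the last required test at first dose**

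Input: the screening window, approximately 8 to 0 weeks before Day 1 (Section 7.1, Visit 1; Section 4.3).

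- One window: 8 × 7 = 56 days.
- Two windows with no repeat test: 2 × 56 = 112 days. This needs screening to overrun, the second 8-week window to be used, and the team to judge a repeat test unnecessary. It is an extreme, not a typical value.
- With a mandatory negative test at V2 before dispensing: 0 days.

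**2. Expected conceptions between the required test and first dose**

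Inputs:

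- Women of childbearing potential among the 362 randomised: assumed 70 to 110, that is 70/362 = 19% to 110/362 = 30%. The protocol gives no figure.
- Contraceptive failure: 1% per year, the ceiling in Section 9.1 for highly effective methods used consistently and correctly.
- Gap from test to first dose: 8 weeks (full window), or an assumed mean of 4 weeks. The protocol gives no mean.
- Allocation 1:1, so half are on valproate.

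Formula: expected number = women × 0.01 × gap in weeks / 52.

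| Gap | Women | Total | On valproate (half) |
|---|---|---|---|
| 8 weeks | 70 | 70 × 0.01 × 8/52 = 0.108 | 0.054 |
| 8 weeks | 110 | 110 × 0.01 × 8/52 = 0.169 | 0.085 |
| 4 weeks | 70 | 70 × 0.01 × 4/52 = 0.054 | 0.027 |
| 4 weeks | 110 | 110 × 0.01 × 4/52 = 0.085 | 0.042 |

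The result is proportional to each input. The 1% ceiling assumes consistent and correct use, so any lapse in contraception raises the figure in proportion.

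**3. The texts side by side**

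| Question | Requires | Allows or omits |
|---|---|---|
| Test at V2? | Negative test to take part, no day fixed (4.3) | Urine optional at V2 (Table 1); no test in the V2 list (7.1) |
| Condition for dispensing? | Valid risk acknowledgement form (7.1, 9.1) | No test at first dispensing in 7.1; conditional urine at later dispensings |
| Delay since the serum test? | Acknowledged in 9.1 | Only an optional urine test is offered |
| Serum or urine? | Serum (5.3, 6.1 item 10, 9.1) | Serum/urine at V1 (7.1); urine if blood is declined (9.1) |

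The protocol does set validity limits and repeats elsewhere. A PANSS rating holds for seven days (Section 8.1.1), and PANSS, vital signs and weight are repeated at V2 under Table 1 footnote 1. The pregnancy test has no validity limit and no required repeat.

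**The case against.** The strongest reply is that this is a considered, risk-based policy with several layers:

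- Only women who still meet all criteria at V2 are randomised, and pregnancy is an exclusion.
- Highly effective contraception is required. Implants must be in place 60 days, and injectables given 14 days, before screening.
- Women who do not meet the prevention programme within the screening period are screen failures.
- Section 9.1 provides for risk review at each time-point, with a urine test if needed, and adopts the MHRA programme and external trial guidance that may itself fix test timing.
- Table 1 does show a urine test at V2, with the same marker as at later visits, so the contrast with those visits exists only in the Section 7.1 lists.

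These points lower the risk, and they are why the expected number is so small. None of them, as written here, is a mandatory test or a limit on test age. Re-reviewing an exclusion criterion without testing relies on the old result. The content of the external guidance is not in the protocol: if it demands a test before first dose, the word optional in the footnote misdirects sites; if it does not, the gap stands. The footnote needs changing either way.

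Two further objections carry some weight. The 112-day figure depends on reassessing the serum criterion on a stale result, so it should be read only as an outer limit. A drug holiday is not in itself a gap in contraception, so that point is secondary.

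On test type, the V1 wording could simply cover both rows of Table 1. That reading does not settle Section 9.1, which says a serum test is needed and then offers urine when blood is declined, without saying whether urine suffices for entry.

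**Conclusion.** The concern holds. As written, the protocol requires no pregnancy test on the day valproate is first dispensed. The only required pre-dose test may be about 56 days old (about 112 days at the extreme), and the text is inconsistent on serum versus urine.

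The expected count of conceptions in the gap is about 0.05 to 0.08 on valproate for a full 8-week window, and about 0.03 to 0.04 with a mean gap of 4 weeks. Both rest on an assumed 70 to 110 women of childbearing potential and the 1% annual failure ceiling; the mean gap is also an assumption. The event is improbable but its harm is irreversible, so this should be fixed. It has no bearing on power or on the primary analysis.

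**What to change.** - **Table 1 and Section 7.1, Visit 2:** make the urine test already scheduled at V2 mandatory, and negative before first dispensing, for women of childbearing potential. Leave it discretionary at later visits.
- **Section 6.5:** require the same negative test before study drug is restarted after a drug holiday.
- **Sections 6.1 (item 10), 7.1 (Visit 1) and 9.1:** state one rule on whether a urine result may replace serum for entry, and use it in all three places.

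The cost is a footnote and visit-list amendment, plus one urine kit per woman of childbearing potential at a visit already held (and one at any restart). The downside is a small added burden and an occasional delayed randomisation.

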5.3 IMP Risks

The Summary of Product Characteristics (SmPC) for 500 mg Gastro-resistant tablets (Sodium Valproate Wockhardt 500mg Gastro-Resistant Tablets, SmPC revised on 19/12/2018) will be the reference document.

Teratogenic risk

There is a potential risk to unborn children associated with valproate treatment. This risk will be minimised in the following ways:

1) Women of childbearing potential will be supported on the Pregnancy Prevention Programme as outlined by the Medicines and Healthcare products Regulatory Agency MHRA [42]. This ensures that they are aware of the potential risks and ensure that they use a highly effective method of contraception that meets the MHRA guidelines. A serum pregnancy test is also conducted as part of the programme. An annual risk acknowledgment form is also needed as part of the programme. The patient's clinical care team and the research team will monitor compliance to the programme. Neither condoms nor oral contraceptives alone are sufficient. Long-term contraceptives (such as copper intrauterine device [IUD] or levonorgestrel intrauterine system and contraceptive implant [progestogen-only implant], or sterilisation) are recommended and patients will be supported to access these if they wish to consider them and are not

already receiving them. If subjects do not meet the pregnancy prevention programme within the screening period after consenting to the study then they will be considered as screen failed and will be rescreened once the requirements are met.

2) An optional urine pregnancy test based on individual patient's risk assessment and circumstances during the trial (e.g. if there is a gap or change in contraception) will be offered.

Abnormal blood cell counts and liver function

There is a potential, rare risk for bleeding, thrombocytopenia, leucopenia and hepatic failure due to valproate. To reduce this potential risk, we will screen-out and exclude people who may be vulnerable to this by reviewing their clinical history and conducting full blood count and liver function tests (LFTs), if indicated, prior to enrolling patients in the study. We will also monitor both tests at 3, and 12 months after initiation of trial drug or if patient exits the trial early.

Other side effects

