Adverse events will be collected for each subject. Subjects should be queried in a non-leading manner, without specific prompting (e.g., "How are you getting on with the medication?"). AEs and SAEs will be monitored throughout the study at all visits. Pretreatment events will be monitored prior to the first dose of study drug.

Clinical Laboratory Assessments

The clinical laboratory tests required by protocol are listed in Section 7.2. Blood and urine samples will be collected for clinical laboratory tests. All clinical laboratory tests will be performed locally except for the post-hoc metabolic, pharmacogenomic & drug level analysis. For detailed instructions regarding clinical laboratory procedures, sampling, and shipping guidelines refer to the study centre laboratory manual based on local clinical laboratory guidelines. Samples will be processed at a local laboratory and only blood samples for post-hoc analysis will be stored at the MRC London Institute of Medical Sciences (LMS), Hammersmith Hospital Campus, London where the CI holds a secondary position. Any value outside the normal range will be flagged for attention of the investigator. The investigator or appropriate designee will indicate whether or not the value is of clinical significance. If a clinical significant abnormality is found in the samples taken during the screening phase then their inclusion should be reviewed. If such were to happen during the treatment phase then they will be recorded as an adverse event (AE) and if needed followed until test(s) have normalized or stabilized.

Vital signs

Measurements will consist of systolic and diastolic blood pressure, respiratory rate and pulse rate. The same arm will be used for all visits to measure blood pressure. Vital signs results assessed as clinically significant by the investigator will be reported as adverse events. Vital signs will be obtained prior to clinical laboratory collections, if any, at their respective time-points.

Height, Weight, and BMI

Height will be measured in meters without shoes and will be recorded at screening. Weight will be measured in kilograms as specified in the Trial Schedule and will be done in street clothes, without shoes and coat/jacket. BMI will be calculated by site staff using the equation BMI = kg/m^2 where kg is a person's weight in kilograms and m^2 is their height in metres squared.

Pregnancy prevention and contraception

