Severe liver damage, including hepatic failure sometimes resulting in fatalities, has been very rarely reported with the use of valproate. In most cases, such liver damage has occurred during the first 6 months of therapy, the period of maximum risk being 2 – 12 weeks (SmPC). A sudden onset of asthenia, malaise, anorexia, lethargy, oedema and drowsiness, which are sometimes associated with repeated vomiting and abdominal pain even prior to the onset of jaundice will trigger liver function test in this period else all patients will have their liver function tested at the 3-month time-point. Transaminitis > 5 times the upper limit of normal value (Grade 3 – CTCAE) will result in review of liver function and if it persists with symptoms of jaundice and relevant clinical context, it will lead to their trial medication stopped if determined clinically necessary. Transaminitis > 10 times the upper limit of normal value (Grade 4- CTCAE[49]) and relevant clinical context will result in trial medication stopped [50].

Fulli Blood Cell count

A common side effect of valproate is a decrease in platelet count, seen in 10-15% of patients taking it long term. A normal human platelet count ranges from 150,000 to 450,000 platelets per microliter of blood. Clinically significant spontaneous bleeding does not usually occur until the platelet count is less than $100,000/\text{mm}^3$. Levels below 75,000/mm³ (Grade 1-CTCAE [49]) will be reviewed in the patient's clinical context and if determined clinically necessary the trial medication will be stopped. Leucopenia and agranulocytosis are uncommon and rare side effect respectively (SMPC) and any Grade 3 CTCAE [49] criteria (less than $2 \times 10^9/\text{Litre WBCs}$, less than $1 \times 10^9/\text{litre}$ neutrophils) in these parameters will lead to trial medication being stopped if determined clinically necessary.

Pancreatitis

Patients experiencing abdominal pain consistent with a clinical diagnosis of pancreatitis will receive investigation and treatment according to NHS standard of care and trial medication will be stopped pending confirmation or exclusion of diagnosis. Confirmation of acute pacreatitits will result in trial medication being permanently stopped. Patients

found to have an elevation in serum amylase >2.0 x upper limit of normal (Grade 3 – CTCAE [49]) will have their trial medication stopped if determined clinically necessary.

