Participants will be followed up until clinical recovery and laboratory results have returned to normal baseline values, or until the event has stabilized. If the investigator believes that an SAE is not related to the study drug, but potentially related to the conditions of the study (such as withdrawal), the relationship will be specified in the narrative section of SAE report form. Pregnancy will be monitored till term and if a live birth occurs, we may request the infant to be followed up to a period of 5 years and monitored for the detection of birth defects and other functional or developmental deficits. After the end of the trial, any subsequent events that may be attributed to treatment will be reported to the MHRA using the yellow card system.

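### Liver function and full blood count before dosing are optional, so a patient not tested at screening starts study drug with no protocol-required pre-dose value

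*Protocol*

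**What the plan says.** The protocol makes the screening LFT and FBC conditional in four places.

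- **Table 1 (section 4.3).** Both rows carry the £ footnote at V1: "To be performed at the discretion of the clinician based on clinical history and medical assessment". The V2 cells are empty. Both tests are then marked without condition at V4, V6 and early exit.
- **Section 4.3, screening period:** "if needed, a blood screen for liver function and full blood cell count will be carried out".
- **Section 5.3, abnormal blood cell counts and liver function.** One sentence gives both the aim and the method. It begins "we will screen-out and exclude people who may be vulnerable to this by reviewing their clinical history" and continues with "conducting full blood count and liver function tests (LFTs), if indicated, prior to enrolling patients in the study".
- **Section 7.1, Visit 1:** "Collect blood sample for clinical laboratory assessments (full blood count, liver function test if needed based on medical history". The Visit 2 list has research blood samples only.

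Two later rules use laboratory results. Section 9.1 (Clinical Laboratory Assessments) says: "If a clinical significant abnormality is found in the samples taken during the screening phase then their inclusion should be reviewed". The same paragraph has a clinically significant abnormality in the treatment phase recorded as an adverse event. Section 9.2 follows participants "until clinical recovery and laboratory results have returned to normal baseline values, or until the event has stabilized".

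**The concern.** Section 5.3 names bleeding, thrombocytopenia, leucopenia and hepatic failure as risks of the drug. The decision to test at screening rests on history and clinical assessment, and so does the liver exclusion (section 6.2, criterion 17). A patient with an abnormality that nobody knows about can pass both for the same reason and start study drug.

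The second issue is attribution. While allocation is blinded, the most direct way for an investigator to tell whether a low platelet count or raised transaminase at V4 is new is to compare it with that patient's own pre-dose result. For a patient not tested at screening, the protocol does not require such a result to exist.

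**Working it through.** No figure in the protocol needs to be reproduced. The check is to follow one untested patient through the schedule and the rules.

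1. **V1.** The clinician sees no indication in the history and orders neither test. This complies with Table 1 and with sections 4.3, 5.3 and 7.1. The wording in 7.1 could be read as making only the LFT conditional, but the £ footnote is on both rows and the screening text in 4.3 makes both conditional.
2. **V2.** No LFT or FBC is listed in Table 1 or in section 7.1. Blood taken here is for post-hoc research and is not reported during the trial. Dosing starts. Protocol-required pre-dose values: 0 LFT, 0 FBC.
3. **Review of inclusion (section 9.1).** The rule acts on an abnormality found in screening samples. With no sample, it has nothing to act on. It is not broken; it is simply not reached.
4. **V4.** This is the first unconditional test. A pre-existing abnormality judged clinically significant now falls under the treatment-phase rule and is recorded as an adverse event. The same abnormality found at V1 would have led to a review of inclusion.
5. **Attribution.** A note to Table 1, applied to the medical history review at V3, asks staff to assess changes from baseline and gives newly arising liver disease as an example. That judgement depends on knowing the starting point. For laboratory values, this patient has none that the protocol required.
6. **Follow-up (section 9.2).** The return to baseline values has no patient-specific reference here, although the rule also allows follow-up to end once the event has stabilised.

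What does not depend on a pre-dose value:

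- The action thresholds in section 9.1 are multiples of the upper limit of normal (transaminases above 5 and 10 times, amylase above 2 times) or absolute counts (platelets below 75,000/mm³, white cells below 2 × 10⁹/L, neutrophils below 1 × 10⁹/L).
- The comparison between randomised arms, the sample size and the primary analysis.

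Upper bound on the burden of testing everyone (section 7.2 gives about 4 ml per test; the flow diagram gives 460 assessed and 362 randomised):

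- Blood: 2 × 4 ml = 8 ml per patient.
- Assays: 2 × 362 = 724 if only randomised patients are counted; 2 × 460 = 920 if all those assessed after consent are counted. Tests already done at discretion or already on file come off these totals.

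**The case against.** The strongest reply is that this is risk-based screening, chosen on purpose and described the same way throughout. Section 5.3 does not promise to find silent abnormalities: its method is to review the history and to test where indicated. Known disease is covered by exclusion criteria 17, 18 and 21, outside records may be obtained where necessary, and symptoms trigger an early LFT. Results can be acted on without a baseline, section 9.2 offers stabilisation as an alternative end to follow-up, and its reference to normal values can be read as the laboratory range. At group level the placebo arm handles attribution, and the data monitoring committee sees unblinded comparative data. Mandatory blood could also deter some patients from a pragmatic trial.

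Most of this stands, and it limits the weight of the point. It does not supply the missing value. The exclusions work only for conditions already known or suspected, and group-level comparison does not tell an investigator whether one patient's result is new. The worry about refusals is limited, because the same tests are required of everyone at V4 and V6 and research blood is already scheduled at V1 or V2, subject to consent and site facilities.

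Three stronger readings are tempting and are not supported:

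- **That the protocol contradicts itself.** It does not; every relevant section makes the screening tests conditional.
- **That optional screening leaves the high-risk weeks unmonitored.** Section 9.1 describes "the period of maximum risk being 2 – 12 weeks" for liver damage, and V4 falls at week 13 ± 2, that is weeks 11 to 15. But this concerns on-treatment monitoring. It does not follow from the £ footnote, and a mandatory V1 test would not change it.
- **That a definite number of patients is affected.** Section 9.1 gives a platelet decrease in 10–15% of long-term users, which is 0.10 × 181 = 18 to 0.15 × 181 = 27 patients allocated valproate. How many of these would lack a pre-dose count depends on the share not tested, which the documents do not give. Letting that share run from 0% to 100% gives 0 to 27, which is uninformative. A decrease is also not the same as a clinically important one.

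**Conclusion.** The point holds as a minor weakness in a deliberate design choice. A patient not tested at screening has no protocol-required pre-dose LFT or FBC. An unrecognised abnormality in that patient bypasses the review of inclusion and, if clinically significant, first appears as an on-treatment adverse event that cannot be compared with the patient's own starting value.

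The consequence is limited to individual safety screening and attribution. It does not bias the treatment comparison or disable the stopping thresholds. Its size cannot be stated: the protocol gives neither the share of patients who would go untested nor a rate of silent abnormalities at entry, and some untested patients will have a recent NHS result on file. The conclusion rests only on the schedule and the rules as written. The case for changing it is that the remedy is cheap.

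**What to change.** Delete the £ footnote in Table 1 and the conditional wording on LFT and FBC in section 4.3 (screening period), section 5.3 and section 7.1 (Visit 1). State that both tests are mandatory for all patients at V1 and that the results are reviewed under section 9.1 before randomisation at V2. Accept a routine NHS result from within the 8-week screening period in place of a new sample. Leave the judgement of clinical significance with the investigator, as now.

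The cost is a short text amendment and at most two routine local assays (about 8 ml) per patient, within the upper bounds worked out above. Patients not otherwise bled at V1 would need an extra draw, and there may be an occasional extra screen failure or refusal. The change supplies the pre-dose value only; whether to add a test during weeks 2 to 12 is a separate decision.
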